****3. ANALYSIS****

3.1 Describe the statistical methods that will be used to address the study aims. For each aim, this will usually include:

- Description of the sample used for the particular analysis
- The variables included in the specific analysis and their role in the analysis
- Numeric summaries computed (e.g., mean, standard deviation, proportion, correlation)
- A summary of data exploration and presentation activities (e.g., generating scatter plots, summary tables)
- Description of statistical tests (e.g., independent samples t-test, Mann-Whitney test), and models constructed (e.g., logistic regression)

Please see our [Examples of Statistical Methods](#).

Describe here:

Note: Please reference the area/pages of an established protocol if you are not writing your own analysis plan.

The analytic study population will consist of patients enrolled during the study period who meet the inclusion/exclusion criteria in Section 2.3 – namely, adults on long-term warfarin therapy who present to the ED with emergent bleeding, or who are in need of urgent invasive surgical procedures. The exposure of interest will be fixed vs. variable dose 4FPCC, to which eligible patients will be randomly assigned in a 1:1 ratio. To evaluate the success of randomization, we will summarize patient demographics and relevant clinical factors by 4FPCC dosing assignment group, and conduct appropriate statistical tests (Fisher's exact test for categorical variables; Wilcoxon test for continuous variables) to identify any differences in the distributions of these factors. If there are no significant differences ($p < 0.05$) found, we will assume successful randomization, and subsequent statistical analyses will not additionally account for covariates.

(Primary) Aim 1: Fixed vs. variable dose 4FPCC and anticoagulation reversal

To evaluate whether fixed dose 4FPCC is acceptably comparable to variable dosing with respect to anticoagulation reversal, as defined by a targeted INR of ≤ 1.5 , we will employ an active-controlled non-inferiority approach to analysis of a randomized trial [D'Agostino 2003]. In order to establish non-inferiority of fixed dosing, we will test the following null and alternative hypotheses:

- $H_0: F - V \leq M$ (Variable dosing is superior to fixed)
- $H_1: F - V > M$ (Fixed dosing is not inferior to variable)

where V = variable dosing, F = fixed dosing, and M = the non-inferiority margin.

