Based on previous literature [D'Agostino 2003, Goldstein 2015] and the available study sample, we propose to set the non-inferiority margin M to -0.1. In other words, if the proportion of warfarin reversal among fixed dose patients is no worse than 10% less than the proportion of warfarin reversal among variable dosed patients, then we will reject the null hypothesis (superiority of variable dosing), and consider the fixed dose to be acceptably non-inferior to variable dosing.

Results to be reported for this aim will consist of the proportion of reversal for each group, the risk difference (RD; the proportion of reversal in fixed group minus the proportion of reversal in variable group), and the risk ratio (RR; the proportion of reversal in fixed group divided by the proportion of reversal in variable group), along with 95% confidence intervals and p-values as appropriate. Non-inferiority will be established if the lower bound of the RD is greater than the pre-specified margin M (-0.1). The primary analysis will use an intent to treat (ITT) approach (fixed vs. variable treatment assignment); however, we will also conduct supplemental analyses using an 'as treated' or 'per protocol' (PP) approach, in which we will compare patients' actual received dose (regardless of assignment) with respect to successful reversal of anticoagulation. We expect the PP approach to complement the primary ITT results, and will be informative particularly if there is non-trivial overlap in dosing by assignment group.

(Secondary) Aim 2: Fixed vs. variable dose 4FPCC and thromboembolic events

Study patients will be followed for 7 days post-administration of 4FPCC for thromboembolic events, as defined in Section 2.12. For this outcome, we will calculate and report the risk (proportion of patients experiencing an event in each group), RD, and RR, with 95% confidence intervals and p-values, as described in Aim 1. While we expect the risk of thromboembolic events to be lower in the fixed dose group, due to the limited number of anticipated thromboembolic events in the study population, the study will not specifically be powered to detect statistically significant differences by dosing group.

(Secondary) Aim 3: Fixed vs. variable dose 4FPCC and costs

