We also expect loss to follow-up to be minimal, as the observation period for a given patient is very short (INR can be evaluated within 15 minutes of 4FPCC administration), and it will be unlikely for patients to leave the hospital prior to collection of relevant measures during an emergency care situation. Though it is possible patients may die during hospitalization, sufficient information should be available for these individuals to contribute to the analysis, with the possible exception of Aim 2 (thromboembolic events).

Power analysis

NOTE: If you are doing a descriptive study (i.e., aside from computing confidence intervals you are not using statistical tests, inferential statistical testing for group comparisons, or statistical models), please complete 3.6 and skip 3.7-3.8.

If you are conducting statistical tests, using statistical inference to compare groups, or are building statistical models, please skip 3.6 and complete 3.7-3.8. **Please see our Example Power Analysis.**

3.6 Provide a measure of the precision of your estimates for key study endpoints, (e.g., 95% confidence intervals on proportions or means), using actual expected estimates.

N/A

3.7 What level of differences observed in your primary endpoints would be considered clinically or practically significant?

As dictated by the active-controlled non-inferiority approach, we will consider the fixed dose of 4FPCC to be non-inferior to variable dosing if the proportion of anticoagulation reversal is no worse than the specified difference margin of -10%.

3.8 What is the power for your primary analysis (and the set of assumptions underlying it: hypothesis addressed, expected pattern of effects with justification for these expectations, analysis used, variables in the analysis, effect sizes, sample sizes, alpha level, one or two-sided test)?

Assuming available treatment group samples of N=24, a non-inferiority margin of -0.1, an alpha significance level of 0.05, an expected targeted reversal proportion in the variable dosing group of 0.77 (pooled estimate from 13 previous studies) [Khorsand 2015], and a true difference in proportions of 0, we will have 22% power to detect non-inferiority of fixed vs. variable dosing of 4FPCC.

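### The lower bound that decides non-inferiority has no stated sidedness or method; read as the limit of a two-sided 95% CI it has about 12–14% power, and the stated 22% fits only a one-sided 5% bound

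*Combined protocol and SAP*

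**What the plan says.** - **Hypotheses (3.1, Aim 1).** The alternative is directional, F - V > M, glossed as "Fixed dosing is not inferior to variable". The margin M is -0.1.
- **Reporting (3.1, Aim 1).** Reversal proportions, RD and risk ratio are reported "along with 95% confidence intervals and p-values as appropriate".
- **Decision rule (next sentence of Aim 1).** "Non-inferiority will be established if the lower bound of the RD is greater than the pre-specified margin M (-0.1"). No confidence level, sidedness or interval method is attached to this bound.
- **Power (3.8).** The form asks for "effect sizes, sample sizes, alpha level, one or two-sided test". The answer gives "an alpha significance level of 0.05" and does not say whether it is one- or two-sided. With 24 per arm, 0.77 reversal on variable dosing and a true difference of 0, it concludes "we will have 22% power to detect non-inferiority of fixed vs. variable dosing of 4FPCC".
- **Sample size and limitations (3.3, 3.9).** The sample size was set by the patients likely to be available in the period. Low power is named as the primary limitation.

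**The concern.** The only interval level near the decision rule is 95%, in the sentence before it. An analyst following the plan would most naturally compute an ordinary two-sided 95% interval for the RD and compare its lower limit with -0.1. That is a one-sided 2.5% test. The power in 3.8 appears to have been computed for a one-sided 5% test. If so, the rule in 3.1 does not have the power that 3.8 gives it.

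More is at stake than the power figure. Whether the bound is taken at one-sided 5% or 2.5% sets the chance of wrongly accepting a fixed dose that is 10 points worse, and it can decide the primary conclusion. The trial is open-label, and section 6.3 says its results will influence whether the hospital adopts fixed dosing. The choice should not be left until the data are in hand.

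**Working it through.** **Inputs (3.1 and 3.8).** n = 24 per arm; reversal 0.77 in both arms (true difference 0); margin -0.1; alpha 0.05, sidedness not stated.

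**Step 1: normal approximation.**
SE = sqrt(2 × 0.77 × 0.23 / 24) = 0.1215, and 0.10 / 0.1215 = 0.823.
- One-sided 5%: Φ(0.823 - 1.645) = 20.6%, close to the stated 22%.
- One-sided 2.5%: Φ(0.823 - 1.960) = 12.8%.

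**Step 2: exact power.** The plan names no interval method, so all 25 × 25 binomial outcomes were enumerated under five common methods without continuity correction. Power is the total probability of the outcomes whose lower bound exceeds -0.10. The last column is the probability that one rule declares non-inferiority and the other does not.

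| Method | One-sided 5% | One-sided 2.5% | Rules disagree |
|---|---|---|---|
| Wald | 22.0% | 14.4% | 7.6% |
| Newcombe | 22.3% | 12.5% | 9.7% |
| Farrington-Manning | 22.0% | 12.2% | 9.8% |
| Miettinen-Nurminen | 20.0% | 12.2% | 7.9% |
| Agresti-Caffo | 20.0% | 12.2% | 7.9% |

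The stated 22% is therefore reproduced at one-sided 5%. At one-sided 2.5% no method checked comes near it. A continuity-corrected Wald bound at 2.5% is lower still: 6.9% by normal approximation and 8.8% by enumeration.

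**Step 3: false-positive rate at the margin (67% fixed, 77% variable).** Under the same five methods it is 5.2–5.8% at one-sided 5% and about 2.5–3.0% at one-sided 2.5%. The rules disagree in about 2.5–3.1% of trials.

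**Step 4: one possible result.** Take 20/24 reversed on fixed and 17/24 on variable dosing. RD = 0.833 - 0.708 = +0.125. The Wald SE is sqrt[(0.833 × 0.167 + 0.708 × 0.292) / 24] = 0.120.
- One-sided 5%: 0.125 - 1.645 × 0.120 = -0.072, above -0.1, so non-inferiority is declared.
- One-sided 2.5%: 0.125 - 1.960 × 0.120 = -0.110, below -0.1, so it is not.

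The other four methods agree: their limits run from -0.076 to -0.080 at 5% and from -0.114 to -0.120 at 2.5%. At 77% against 77%, outcomes that pass at 5% under all five methods and fail at 2.5% under all five make up 5.6% of trials.

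**Step 5: the enrolment ceiling of 60 (30 per arm).** Power is 24.0–24.2% at one-sided 5% and 14.1–16.3% at one-sided 2.5%. The gap remains.

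**The case against.** The strongest reply is that the plan can be read coherently. The alternative is directional, alpha is 0.05, 22% reproduces at one-sided 5%, and 95% is the complement of 0.05. A one-sided 95% bound fits all of these. This stands as a possible reading, but the text does not state it. Direction alone does not settle the level, because the lower limit of a two-sided 95% interval tests the same directional hypothesis at 2.5%.

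It is also fair to say that the level is not wholly missing: 95% is named in the sentence before the rule. What is open is the sidedness and the method. Aim 2 refers back to the same intervals ("with 95% confidence intervals and p-values, as described in Aim 1") for a comparison with no margin, but this adds little, since the phrase may refer only to the list of summaries.

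The power gap changes neither enrolment nor the limitation already disclosed in 3.9. That stands too, but disclosing low power does not fix the error rate of the test.

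Finally, the 8–10% disagreement belongs to one scenario, and in about 90% or more of trials at 77% against 77% both rules give the same verdict. The 20/24 against 17/24 example is one where fixed dosing looks 12.5 points better.

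A reader might infer that 22% is a miscalculation, or that 3.1 and 3.8 flatly contradict each other. The documents support neither: the figure is right for a one-sided 5% test, and a contradiction arises only once the bound is taken as two-sided.

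**Conclusion.** The concern holds as a missing link between the decision rule and the power calculation, and should be fixed. On the ordinary reading of 3.1, power is about 12–14% without continuity correction and lower with it, so 22% would be overstated by about 8–10 points. On a one-sided 95% reading, 22% is correct for some methods and about 20% for others.

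The more important result is that the one-sided error rate of the primary conclusion is left at either 5% or 2.5%. The choice changes the verdict in about 8–10% of trials if both arms reverse 77%, and in about 2.5–3% if fixed dosing is truly 10 points worse. Of the results that pass at 5% when both arms reverse 77%, between a third and a half would fail at 2.5% (7.6/22.0 = 35% for Wald; 9.8/22.0 = 45% for Farrington-Manning).

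These figures assume 24 evaluable patients per arm, the plan's 77% reversal rate on variable dosing, and bounds without continuity correction.

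**What to change.** Before any outcome data are seen, state in 3.1 the level, sidedness and interval method of the decision bound, and make 3.8 match. Two wordings would do, and the choice belongs to the authors:

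- **(a)** Declare non-inferiority if the lower limit of the two-sided 95% CI for the RD (one-sided alpha 0.025, named method) exceeds -0.1. Restate the power in 3.8 as about 12–14%, using the value for the named method.
- **(b)** Declare non-inferiority at one-sided alpha 0.05, using the lower limit of the two-sided 90% CI (named method). Keep 22% in 3.8, or about 20% if Miettinen-Nurminen or Agresti-Caffo is named, and label the reported two-sided 95% CI as descriptive.

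If a continuity-corrected method is chosen, power must be recomputed, because it falls below these ranges. The change is wording only and enrolment stays the same. Option (a) costs a less favourable stated power. Option (b) means stating openly a 5% one-sided error rate, with an actual false-positive rate of about 5–6% at a true 10-point deficit rather than 2.5–3%.

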3.9 What are the limitations of the proposed approach and analysis?

The primary limitation will be low statistical power to reject the null hypothesis (superiority of variable dose 4FPCC), given limited sample size. Additionally, due to the nature of the intervention, blinding of treatment dosage assignment will not be feasible. Finally, patient follow-up for thromboembolic events at 7-days post 4FPCC administration may not be achieved in all patients due to discharge.

3.10 Please name the people who completed the analysis section of this application.

[name], MPH

3.11 Please name the people who will summarize data and conduct statistical analysis.

[name], MPH, and/or another member of the HealthPartners Institute Research Methodology Group.

****5. DISSEMINATION****

5.1 What are your plans for publication, including target journals?

We plan to publish our results following study completion. The target journals include the American Journal of Emergency Medicine, Thrombosis Research, Hematology, and Journal of Thrombosis and Hemostasis.

5.2 What plans do you have to share results or translate results to care delivery at HP or for HP personnel?

[name] will be presenting preliminary results at the Midwest Pharmacy Residency Conference, to the pharmacy staff at Regions Hospital as well as, to the emergency medicine and hematology/oncology departments. Our goal is for the data to be incorporated in the development of future policy changes regarding reversal of warfarin anticoagulation.

****6. ENVIRONMENT****

6.1 Where will the study be conducted? Why is the proposed location appropriate for study?

The study will be conducted at Regions Hospital. This location is appropriate as this study is designed to assess the efficacy of fixed versus variable dosing of 4FPCC in emergent warfarin reversal.

6.2 How will the results of this study impact the health of HealthPartners members and the community? Be specific as to whether and how you see any clinical application as a result of this study.

This study has the potential to impact future protocol and prescribing habits of 4FPCC if results show that fixed dosing is as efficacious as variable dosing.

6.3 Does the treatment strategy (drug or service) proposed in the study commit HP to covering or continuing to provide the treatment or program support after the study is completed?

The results of the prospective, randomized study will influence whether Regions Hospital adopts a fixed dosing protocol for 4FPCC administration.

****7. OTHER REVIEW****

7.1 Has this study been submitted for other review and/or received approval/rejection previously, including but not limited to: Federal, collaborative agency, previous HealthPartners (rejected), or other funding sources (e.g., nonprofit foundation review)?

X	No
	Yes (Provide dates of submission and status of review [approved, pending, or rejected])

****8. DATA ACCESS REQUEST****

These questions must be completed if you are accessing HP/Regions data or if your study involves a HealthPartners Institute programmer. You will need to work with an Institute programmer to complete this form. Please contact [name] [contact]) or [name] [contact]) for assistance.

If you are not proposing the access HP/Regions data (e.g. Animal Study), you may check "N/A" below.

8.1 What is the name of the programmer helped you complete this section?

N/A

8.2 Will you need to add a programmer to your study team?

X	No
	Yes

8.3 Considering your inclusion/exclusion criteria described in 2.3, what specific data will you need?

N/A

8.4 What years of data are needed?

Data will be collected prospectively.

8.5 Will any of the study data be shared or transferred to others within HealthPartners?

Only members of the study team will access data.

8.6 Will any study data be shared or transferred to others outside of HealthPartners?

X	No
	
Yes - mark which method you will use to share study data:
 
 E-transfer
 
 Secure website/portal
 
 Other secure, encrypted method. Describe below.

8.7 Data Sources (please mark all known data sources)

Mark (X)	Data Source	Mark (X)	Data Source
	EWIS – Claims Data		Registries (chronic condition, disease)
	RDW (Research Data Mart) – historical medical, dental, state death data		Inpatient Case Management data (i.e., Care Guide, Care Partner)
	Claims/Mumps/Cache		Paper Medical Chart
X	EPIC (Electronic Medical Record)		Provider's own source (own patient's chart, provider or department/hospital registry)

	EDR (Electronic Dental Record)	Geriatric department data (i.e., transitional, long term care database)
	EDR Reporting	Data directly from contracted clinics
	New Subject Survey	VDW (Virtual Data Warehouse)
	MEDIPAC System (Regions Billing System)	Consolidated Network Provider (CPN)
	Physician Services Department Data	Health Behavior Group Data (e.g., 10,000 steps, HRA)
	MN State Death Data	MN State Birth Data
	Misys/Sunquest (Lab production system)	Clarity (Epic Reporting Database)
	Other (Please describe):	

8.8 Exclusion Lists: Institute programmers are required to review and apply the following privacy requirements to study patients and their wishes regarding access to medical record information.

Mark X	Exclusion List
	HealthPartners Institute Exclusion List which excludes persons from all medical research. This should be used for all studies. Applies to all data used internally and externally.
	Gramm-Leach-Biley Opt-Out List: (if known; sometimes this can be determined after a study starts). Applies to identifiable data being sent externally.
	Consent for Treatment-Payment-Operations (TPO) Opt-Out List: (if known; sometimes this can be determined after a study starts). Applies to identifiable data being sent externally.

8.9 Data Elements (Please mark all elements that will be used/ accessed during the study):

Mark (X)	Data Elements
X	Name
	Address
	Telephone Number (any)
	Fax Number
	Certificate/license number (i.e., DEA number, professional license number)
	Email address
	Device identifier or serial number
	URL or IP address (web addresses)
	Full face photos, biometric identifiers, or other images
	Health Plan beneficiary number (or family contract number)
X	Date of Birth
	Vehicle identification or serial number
X	Medical Record number (or any personal record identifier)

8.10 Data Content (Please mark all content areas that apply to your study)

Mark (X)	Data Content
X	Demographic: age and gender

	Health Plan enrollment information (i.e., dates, coverage)
X	Diagnoses - Medical
X	Procedures - Medical
	Mortality Data
X	Lab Results
X	Prescriptions/ Medications
X	Dates of Service (treatment)
X	Facility or Provider Identifier / Characteristics (e.g., specialty, FTE, Clinic)
	Birth Certificate Data
	Pathology / Tissue Type
X	Financial data
X	Provider notes
X	Vitals – height, weight, BP, etc
	Social history – tobacco use, etc.
X	Other Clinical data
X	Other: please describe: the attending physician will be recorded

